5.5. Prior and Concomitant Medication

Prior and concomitant medications will be coded using the World Health Organization (WHO) Drug B3-March Format, 2020 version or later. These medications will be further classified as follows.

- Prior medication: are defined as those medications taken prior to the first dose of double-blind treatment.
 - Non-IBS prior medication
 - IBS prior medication
- Concomitant medication: are defined as those taken on or after the first dose of double-blind medication but prior to the last dose of double-blind medication + 14 days. If medications started prior to double-blind medication and were ongoing during the Double-Blind Period, those medication will be considered as concomitant medication as well. See [Table 1](#).
- Post medication: medication taken after last dose of double-blind medication + 14 days

Except for Prior IBS medication, the number and percentage of subjects taking prior non-IBS medications and non-rescue concomitant medications will be summarized overall by ATC (Anatomical Therapeutical Chemical) Levels 2 and 4 for all subjects in the SAF. Prior IBS medications and rescue concomitant medications will be summarized by ATC Levels 2, 4 and Preferred Term in the SAF. Prior medications, IBS rescue concomitant and non-rescue concomitant medications will be listed for all subjects in the SAF. Post medication if any will be listed only.

5.5.1. Rescue Medication

Use of rescue medication will be collected on the daily diary (i.e., subjects will respond to prompts asking if any rescue medication was taken for abdominal pain or stool or pain/stool symptoms). The proportion of subjects who used rescue medication and the reason for the medication will be summarized by treatment groups. This data will be summarized for the efficacy populations.

Note, protocol Amendment 3 clarified that rescue medications should only be used beginning at Day 1 (Visit 3).

6. EFFICACY ANALYSIS

In general, the FAS will be used for all analyses of efficacy endpoints unless stated otherwise.

6.1. Primary Efficacy Analyses

6.1.1. Primary Analysis

The primary efficacy endpoint of proportion of IBS-D subjects who are API weekly responders with $\geq 30\%$ improvement from Week 1 through Week 12 is defined in the [Section 4.3.1](#).

The number and percentage of responders and non-responders will be tabulated by treatment and visit. The treatment comparison will use a Cochran-Mantel-Haenszel (CMH) common risk difference estimate stratified by baseline abdominal pain (< 6 vs. ≥ 6) strata per randomization stratification [11] with weights proposed by Greenland and Robins [6], which is calculated as follows:

$$\hat{\delta}_{MH} = \frac{\sum_{i=1}^u w_i \hat{\delta}_i}{\sum_{i=1}^u w_i}, \text{ where}$$

$\hat{\delta}_i = \frac{x_i}{n_i} - \frac{y_i}{m_i}$ denotes the risk difference in stratum $i, i = 1, \dots, u$

$w_i = \frac{n_i \cdot m_i}{n_i + m_i}$ denotes the weight of stratum $i, i = 1, \dots, u$

x_i denotes the number of subjects with event in treatment₁ in stratum $i, i = 1, \dots, u$

y_i denotes the number of subjects with event in treatment₂ in stratum $i, i = 1, \dots, u$

n_i denotes the number of subjects on treatment₁ in stratum $i, i = 1, \dots, u$

m_i denotes the number of subjects on treatment₂ in stratum $i, i = 1, \dots, u$

The estimated variance of $\hat{\delta}_{MH}$ is calculated as:

$$\widehat{var}(\hat{\delta}_{MH}) = \frac{\sum_{i=1}^u L_i}{(\sum_{i=1}^u w_i)^2}$$

where $L_i = \frac{x_i(n_i - x_i) m_i^3 + y_i(m_i - y_i) n_i^3}{n_i \cdot m_i \cdot (n_i + m_i)^2}, i = 1, \dots, u$

Assuming a normal distribution of $\hat{\delta}_{MH}$, an approximate 90% CI is given as follows, where $z_{0.95}$ is the 95% quantile of the standard normal distribution:

$$CI = \left[\hat{\delta}_{MH} \pm z_{0.95} \cdot \sqrt{\widehat{var}(\hat{\delta}_{MH})} \right]$$

Also, the approximate p-value can be calculated using the following:

$$p\text{-value} = 2 \cdot \Pr \left[Z > \left| \frac{\hat{\delta}_{MH}}{\sqrt{\widehat{var}(\hat{\delta}_{MH})}} \right| \right], \text{ where } Z \sim N(0, 1)$$

If there is a stratum for a treatment group that has 0 subjects in it, the 0 count will be replaced by 0.5 in order to prevent dividing by 0 in the above equations, as suggested in Greenland and Robins.

The estimated common risk difference, and associated p-value and 2-sided 90% confidence interval will be tabulated. The stratified strata is based on the baseline abdominal pain score which is the average from 7 days immediately prior to the baseline visit. If more than 10% mis-classification of the stratification factors (randomization stratification vs. actual stratification values) happens a sensitivity analysis will be carried out to repeat the primary analysis where the actual stratification will be used in the model (See [Section 6.1.2](#)).

The number and percentage of responders with $\geq 30\%$ improvement over Weeks 1-2, Weeks 1-4, Weeks 1-8 and Weeks 1-12 will be summarized by treatment. The proportion of subjects who meet the Weekly responder criteria at each week will be plotted by treatment.

To assess the impact of missing data, a categorical summary of missing pain and bowel movement diary day entries, summarized by week, will be provided with the categories of none, 1-2, > 2 days, > 3 . The denominator used for the percentages will be the number of subjects who completed diaries for the given week.

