9.2. Sample Size Determination

In total, approximately 200 subjects will be randomized in a 1:1 ratio to receive 1 of the following study drugs:

- Vibegron 75 mg (N = 100)
- Placebo (N = 100)

At most, 50% of randomized subjects (approximately 100 subjects total [50 per treatment arm]) will have IBS-M; and at least 50% of randomized subjects (approximately 100 subjects total [50 per treatment arm]) will have IBS-D, and the IBS-D subgroup will be used for the primary endpoint analysis.

Assuming a total of 10% of subjects will discontinue prior to Week 12 (for any reason), there will be a minimum of approximately 90 evaluable IBS-D subjects (45 in the vibegron arm and 45 in the placebo arm) at the end of Week 12. The study has approximately 60% power to detect a between-group treatment difference of 20% in proportion of abdominal pain responders at a 2-sided test at the $\alpha = 0.10$ level assuming a responder rate of 51% versus 31% for vibegron and placebo, respectively. The assumptions were based on results from a solabegron study female subgroup analysis [Kelleher, 2008].

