1.2.2. Randomization and Blinding

Randomization will occur centrally using an interactive voice or web response system (IxRS) using central, stratified block randomization. Randomization will be stratified based on the following stratification factors:

- Baseline abdominal pain intensity score (<6 vs ≥ 6) on a 0 to 10 numeric rating scale [NRS], and
- IBS subtype (IBS-D vs IBS-M)

For this study a double-blind/masking technique will be used: vibegron and its matching placebo will be packaged identically so that treatment blind/masking is maintained. The subject, the Investigator, and Sponsor personnel or delegate(s) who are involved in the treatment or clinical evaluation of the subjects will not be aware of the treatment group assignments.

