6.2. Secondary Efficacy Analyses

[figure not shown]
The secondary efficacy endpoint GIS responder at Week 12 is defined in [Section 4.3.1](#). The proportion of responders will be analyzed similarly as described for primary endpoints using CMH for IBS-D and IBS_M subjects. When all subjects are included for the analysis, additional IBS subtype (IBS-D vs. IBSM will be used for stratification as well. The number and percentage of responder and non-responder for IBS-D, IBS-M and all IBS subjects will be tabulated by treatment and visit. GIS response data will be listed.

[figure not shown]
The secondary efficacy endpoints of proportion of IBS-D subjects who are API weekly responders with 40% improvement and API weekly responders with 50% improvement from Week 1 through Week 12 are defined in the [Section 4.3.1](#). The similar statistical analyses described in primary efficacy endpoint will be performed for these API weekly responders including subgroup analysis.

[figure not shown]
The secondary efficacy analyses will be primarily based on the FAS, unless stated otherwise.

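### The zero-count rule in SAP 6.1.1 gives an empty arm of a stratum an invented response rate with positive weight; it is wrong as written, but unlikely to be used in the primary analysis and small there.

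*SAP*

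**What the plan says.** SAP 6.1.1 specifies a "common risk difference estimate stratified by baseline abdominal pain" (below 6 versus 6 or above), with strata as randomised. For stratum i, with x of n responders in one arm and y of m in the other, the difference is δ = x/n − y/m, the weight is w = n·m/(n+m), and a variance term L is summed and divided by the squared total weight. For a treatment group with no subjects in a stratum it adds that "the 0 count will be replaced by 0.5 in order to prevent dividing by 0 in the above equations". The stated purpose is to avoid division by zero, and the rule is attributed to the methods paper cited for the weights. The symbols x and y are defined by the phrase "denotes the number of subjects with event in" the arm and stratum; the rule does not mention them.

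The same method is reused for:
- the per-protocol set (6.1.2.1);
- a repeat on actual strata if misclassification exceeds 10% (6.1.2.4);
- each pain stratum separately (6.1.3);
- the secondary responder endpoints (6.2), where "When all subjects are included for the analysis, additional IBS subtype" becomes a further factor, giving four cells;
- FAS-M (output tables, 11.1.1).

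Neither document has a rule to drop or pool a stratum.

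**The concern.** A stratum with subjects in only one arm cannot inform a between-arm difference, so a stratified estimator should ignore it. The SAP instead puts half a subject in the empty arm and then treats that arm's response rate as observed. The surviving arm's rate then enters the estimate as if it were a treatment contrast, and the added weight comes with almost no added variance.

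The study's stated aim is to estimate the treatment effect (Protocol 9.1; SAP 1.2.3), so what is at stake is the point estimate and its 90% interval. The rule is prespecified and would be programmed as it stands.

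**Working it through.** **Plan figure.** The documents give no figure for this rule. The nearest is the power statement (Protocol 9.2): 45 per arm, 51% versus 31%, two-sided α = 0.10, about 60%. With pooled rate 0.41, the null SE is √(2·0.41·0.59/45) = 0.1037 and the alternative SE is √((0.51·0.49 + 0.31·0.69)/45) = 0.1015. Power = Φ((0.200 − 1.645·0.1037)/0.1015) = 61.4%. It reproduces. I use these rates only to choose realistic counts (51% of 45 ≈ 23; 31% of 45 ≈ 14).

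**Algebra.** w·δ simplifies to (x·m − y·n)/(n+m). With n = 0 and x = 0, both this and w are 0, so the stratum leaves numerator and denominator. With n = 0.5 and x = 0:
- rate = 0/0.5 = 0%, so δ = −y/m;
- w = 0.5·m/(0.5+m): 0.333 for m = 1, 0.455 for m = 5, always below 0.5;
- x(n−x) = 0, so the empty arm adds nothing to L.

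If x is also set to 0.5, the rate is 100% and x(n−x) is still 0.

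**Example A (assumed counts).** Vibegron 23/45 and empty; placebo 12/40 and 3/5.
- Stratum 1: w = 45·40/85 = 21.176, δ = 0.2111, L = 4.8444.
- Stratum 2 under the rule: w = 0.4545, δ = −0.600, L = 0.0099.
- Dropped: 0.2111, SE = √4.8444/21.176 = 0.1039.
- Rule: (4.4706 − 0.2727)/21.631 = 0.1941, SE = √4.8544/21.631 = 0.1019.
- Replacing 0.5 by 0.0001 returns 0.2111, the dropped value.

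**All examples (assumed counts; difference in points).**

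| Case | Dropped | Rule, events left at 0 |
|---|---|---|
| A, as above | 21.1 (p = 0.042) | 19.4 (p = 0.057) |
| B: 23/45 v 14/45; vibegron empty, placebo 2/5 | 20.0 (p = 0.049) | 18.8 (p = 0.059) |
| C: 23/45 v 14/45; placebo empty, vibegron 3/5 | 20.0 (p = 0.049) | 20.8 (p = 0.037) |
| D: 5/10 v 3/10; vibegron empty, placebo 3/4 | 20.0 (p = 0.35) | 12.2 (p = 0.54) |
| E: one stratum only; vibegron empty, placebo 3/5 | not estimable | −60.0 (p = 0.006) |

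With the event count also set to 0.5, A becomes 21.5 and B 20.8, so the shift changes sign. In E the SE is 0.219 = √(0.6·0.4/5), the placebo arm's own standard error.

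**Reachability.** Allocation is 1:1 "using central, stratified block randomization" on pain and subtype. With block size b, an empty arm as randomised can face at most b/2 subjects, so 5 versus 0 needs b ≥ 10 and 4 versus 0 needs b ≥ 8. Block size is not stated. Take 90 IBS-D subjects and a pain stratum holding an assumed share q:
- simple 1:1 allocation: the chance of one empty arm is 18.5% (q = 5%), 2.0% (10%) and 0.015% (20%);
- blocks of 4 (assumed): only strata of 1 or 2 subjects can have an empty arm, so the chance is P(1) + P(2)/3. That is 0.0468 + 0.1097/3 = 8.3% at q = 5%, and 0.0008 + 0.0038/3 = 0.2% at q = 10%.

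**The case against.** The best defence is that the design almost rules out the trigger. The CMH strata are the randomisation strata, blocked centrally, and nothing in the documents suggests a pain stratum as small as 5%. The four GIS cells are blocked too, and a missing GIS answer counts as non-response (SAP 4.3.1.2), so dropout alone need not empty a cell. All of this stands.

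Some rule is also needed, because the formulas contain 0/0 when n = 0, and the SAP did prespecify one. That stands as well, but excluding the stratum meets the same need without inventing data. The logistic regression in 6.1.2.2 needs no substitution and is a partial backstop, although it gives an odds ratio and is labelled exploratory.

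Four stronger readings are tempting, and the documents do not support them:
- *The primary result is likely to be biased.* The blocking makes this improbable. The 18.5% figure assumes simple allocation and a 5% stratum; the first is not this design and the second is not in the documents.
- *The rule can turn a positive result negative.* The move from 0.042 to 0.057 in example A crosses 0.05, which this study does not use. The nominal level is 10% with 90% intervals (Protocol 9.4.2), all efficacy analyses are descriptive (SAP 4.1.2), and A to C stay below 0.10 either way.
- *The bias always runs against the empty arm.* That holds only if the event count stays at 0. This is the literal reading, but the SAP does not settle it.
- *The SAP misstates its source.* The cited paper cannot be checked from these documents, and nothing here depends on it.

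**Conclusion.** The rule is wrong as written, with low severity. Whenever it is applied, it adds an invented rate with positive weight and no variance for the empty arm, in place of a stratum that should contribute nothing.

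At FAS-D size the shift is about 1 to 2 points in realistic cases, against a 90% interval half-width of about 17 points (1.645·0.1039). The standard error falls by about 2% (0.1039 to 0.1019), and no conclusion at the 10% level changes in the examples. It will probably never be triggered in FAS-D or the four-cell GIS analysis.

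The less protected uses are:
- the per-protocol set, where exclusions after randomisation can break block balance;
- the actual-strata repeat (6.1.2.4), since blocks do not balance actual strata;
- FAS-M if it turns out small, since IBS-M has a cap but no minimum;
- the within-stratum estimates (6.1.3), where the trigger is no likelier than in the parent set but no other stratum dilutes the error.

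The algebra rests only on the SAP's formulas. The sizes rest on assumed counts, and the 10-per-arm case D matches no sample size in the plan. The chances rest on assumed stratum shares and block size.

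**What to change.** Replace the sentence in SAP 6.1.1 with: *A stratum with no subjects in one arm has w_i = 0 and L_i = 0 and is excluded from the estimate and variance, with its subjects reported; a single-stratum analysis with an empty arm is reported as not estimable.* State that this applies wherever the CMH method is reused (6.1.2, 6.1.3, 6.2 and the FAS-M tables). Pooling with the other pain stratum would also be acceptable if that rule is prespecified.

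The cost is one SAP sentence and a small programming change before unblinding. Data collection, sample size and the power figure are unaffected.

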6.1.2. Sensitivity Analysis

The following sensitivity analyses will be performed:

6.1.2.1 API weekly responder $\geq 30\%$ improvement from Week 1 through Week 12 using PPS-D

The treatment comparison of proportion of IBS-D subjects who are API weekly responders with $\geq 30\%$ improvement from Week 1 through Week 12 will be performed using CMH described in the primary analysis based on the PPS.

6.1.2.2 API weekly responder $\geq 30\%$ improvement from Week 1 through Week 12 using Logistic Regression

In addition, Logistic regression will be used as a sensitivity analysis to analyze the API weekly responder with $\geq 30\%$ improvement over Weeks 1-12 based on the FAS but will be considered

exploratory. Responder proportion over Weeks 1-12 will be modeled using treatment and baseline abdominal pain (< 6 vs. ≥ 6) strata per randomization stratification fixed effects. A summary table will present the estimated incidence for each treatment along with the odds ratio, and associated corresponding 90% CI and p-value for the treatment comparison. Wald statistics and Wald confidence limits from SAS PROC LOGISTIC will be used for the test and the construction of 90% CI.

An example of the SAS code for the base procedure is given below if responder is assigned to 1 and no-responder is assigned to 0.

6.1.2.3 API weekly responder accounting for the use of rescue medication

Additionally, a sensitivity analysis of the primary analysis will be performed to assess the impact of subjects receiving rescue medications for pain where subject's diary will be considered non-evaluable on the days that they received rescue medications. This analysis approach will also be performed in FAS-D to assess the treatment comparison of API weekly responders $\geq 40\%$ and $\geq 50\%$ improvement, respectively.

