6.5.3. Rescue Medicine

Rescue medications should only be used starting at Day 1 (Visit 3) or after. The following rescue medications may be used:

For pain

- Equivalent of ibuprofen 400 mg twice daily or less
- Low-dose acetaminophen 500 mg three times daily or less
- Low-dose aspirin (\leq 325 mg daily)

For constipation (not thought to affect IBS pain)

- Polyethylene glycol
- Bisacodyl (no more than one 5-mg dose weekly)

For diarrhea (not thought to affect IBS pain)

- Loperamide (up to 4 mg four times daily)

Rescue medications will not be provided by the Sponsor.

Use of rescue medication will be collected on the daily diary (ie, subjects will respond to prompts asking if any rescue medication was taken for abdominal pain or stool symptoms). During the subsequent subject visit, the details of the rescue medication will be collected for inclusion on the concomitant medication eCRF page, as needed.

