8.2.1. Symptom Diaries

Subjects will complete 2 diaries daily, a Bowel Movement Diary and a Pain Diary. The Bowel Movement Diary will be event-driven (ie, subjects will record events as they occur) and will capture bowel movement frequency and form, bowel urgency, and recurrent bowel movements. The Pain Diary will prompt subjects each evening to answer a question regarding worst abdominal pain for the past 24 hours using the 0- to 10-point NRS to rate pain and to capture use of rescue medications.

Subjects will receive the diaries and be trained on their use at the start of the Run-in Period (Visit 2). At subsequent visits, subjects will be re-instructed or retrained as needed. Subjects

must be able to complete the diaries to be eligible for the study. Further details on training and the use of the diaries are provided in a separate manual.

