4.3.1.1. API Weekly Responder

To derive API Weekly Responder during various week intervals, the initial two steps should be followed to derive (1) Weekly average worst abdominal pain (WAP) score; (2) Weekly Responder status by week

Step 1:

- Weekly average is defined as the sum of WAP scores on the NRS (0-10) in the 7 days immediately prior to baseline visit (Day 1) or each of post-baseline Weeks (Week 1-Week 12), divided by the number of days with non-missing pain diary entries during the 7 days. Weekly average will be set missing if there are more than 2 missed diary days over the past 7 days.
- API Weekly Responder with $\geq 30\%$ improvement at each week (i.e., Week 1, Week 2, Week 3, ..., Week 12) is defined as a subject who experiences a decrease in the weekly average of WAP score of at least 30% compared with the baseline weekly average. To qualify as a responder for the specific week, a subject must have at least 5 days of non-missing pain diary entries during the week (i.e., ≥ 5 of 7 days). A Subject will be assigned as non-responder for the specific week if the weekly average is missing.

Similarly, the API Weekly Responder will be further derived based on more stringent measures of weekly reduction as below:

- API Weekly Responder with $\geq 40\%$ improvement at each week (i.e., Week 1, Week 2, Week 3, ..., Week 12) is defined as a subject who experiences a decrease in the weekly

average of WAP score of at least 40% compared with the baseline weekly average. To qualify as a responder for the specific week, a subject must have at least of 5 days of non-missing pain diary entries during the week (i.e., ≥ 5 of 7 days).

- API Weekly Responder with $\geq 50\%$ improvement at each week (i.e., Week 1, Week 2, Week 3, ..., Week 12) is defined as a subject who experiences a decrease in the weekly average of WAP score of at least 50% compared with the baseline weekly average. To qualify as a responder for the specific week, a subject must have at least of 5 days of non-missing pain diary entries during the week (i.e., ≥ 5 of 7 days).

Step 2:

Then API Weekly Responder will be derived during different treatment intervals using primary criteria as an example below:

API Weekly responder with $\geq 30\%$ improvement over 12 weeks (i.e., from randomization through to Week 12) - primary efficacy endpoint

- To qualify as an overall API Weekly Responder from randomization through to Week 12 (Weeks 1-12), a subject must satisfy the following criteria:

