 - Must meet the API Weekly Response criteria $\geq 30\%$ improvement on $\geq 50\%$ of weeks, i.e., success on 6 or more weeks during the past 12 weeks
 - Must have had ≥ 60 diary days over the past 12 weeks

API Weekly responder from randomization through to Week 2 (Weeks 1-2)

- To qualify as an API Weekly Responder from randomization through to Week 2, a subject must satisfy the following criteria:
 - Must meet the API Weekly Response criteria on more than 50% of weeks, i.e., success on 1 or 2 weeks during past 2 weeks
 - Must have had ≥ 10 diary days over the past 2 weeks

API Weekly Responder from randomization through to Week 4 (Weeks 1-4)

- To qualify as an API Weekly Responder over 4-week interval, a subject must satisfy the following criteria:
 - Must meet the API Weekly Response criteria on more than 50% of weeks, i.e., success on 2 or more weeks during past 4 weeks
 - Must have had ≥ 20 diary days over the past 4 weeks

API Weekly Responder from randomization through to Week 8 (Weeks 1-8)

- To qualify as an API Weekly Responder over 8-week interval, a subject must satisfy the following criteria:
 - Must meet the API Weekly Response criteria on more than 50% of weeks, i.e., success on 4 or more weeks during past 8 weeks
 - Must have had ≥ 40 diary days over the past 8 weeks

The secondary efficacy endpoints of Weekly API Responder with either $\geq 40\%$ or $\geq 50\%$ improvement will be classified using the same rules above.

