
Title		Analysis Set	Programming Note	Deliverable
14.2.1.3.1	API Weekly Responder over Weeks 1-12: $\geq 30\%$ Improvement Sensitivity Analysis (Logistic Regression) – IBS-D Subjects	FAS-D		EOS
14.2.1.3.2		FAS-D	Include all intervals but over Weeks 1-12 in the front; The subject is considered a non-responder for the days receiving pain medication	EOS
14.2.1.4	API Weekly Responder Analysis (CMH): $\geq 40\%$ Improvement – IBS-D Subjects	FAS-D	Include all intervals but over Weeks 1-12 in the front	TL, EOS
14.2.1.5		FAS-D	Include all intervals but over Weeks 1-12 in the front; The subject is considered a non-responder for the days receiving pain medication	EOS
14.2.1.6	API Weekly Responder Analysis (CMH): $\geq 50\%$ Improvement – IBS-D Subjects	FAS-D	Include all intervals but over Weeks 1-12 in the front	TL, EOS
14.2.1.7		FAS-D	Include all intervals but over Weeks 1-12 in the front; The subject is considered a non-responder for the days receiving pain medication	EOS
14.2.1.8	API Weekly Responder Analysis (CMH): $\geq 30\%$ Improvement -IBS-M Subjects	FAS-M		TL, EOS
14.2.1.9 – 14.2.1.10		FAS-M		EOS
14.2.1.11	API Weekly Responder Analysis (CMH): $\geq 30\%$ Improvement -IBS All Subjects	FAS		TL, EOS
14.2.1.12 – 14.2.1.13	API Weekly Responder Analysis (CMH): $\geq 40\%/50\%$ Improvement -IBS All Subjects	FAS		EOS

Title		Analysis Set	Programming Note	Deliverable
14.2.1.14 – 14.2.1.16	API Weekly Responder over Weeks 1-12 Subgroup Analysis by API Strata (CMH): $\geq 30\%/40\%/50\%$ Improvement – IBS-D Subjects	FAS-D	Percentages are based on the n within each subgroup	EOS
14.2.1.17	API Weekly Responder $\geq 30\%/40\%/50\%$ Improvement over Weeks 1-12 by Subgroup	FAS	Descriptive summary. Subgroups are listed under SAP subgroup section; include three thresholds	EOS
14.2.2.1	Global Improvement Scale Responder Analysis (CMH) – IBS-D Subjects	FAS-D	Include all Weeks but Week 12 in the front. Include a footnote, "A responder is defined as a subject who answered that their symptoms were either moderately relieved or significantly relieved."	TL, EOS
14.2.2.3	Global Improvement Scale Responder Analysis (CMH) – IBS-M Subjects	FAS-M	Include all Weeks but Week 12 in the front	EOS
14.2.2.4	Global Improvement Scale Responder Analysis (CMH) –All Subjects	FAS	Include all Weeks but Week 12 in the front	EOS
14.2.2.5	Shift Table of Global Improvement Scale from Baseline - IBS-D Subjects	FAS-D	Include all Weeks but Week 12 in the front	EOS

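### Rescue sensitivity analysis (SAP 6.1.2.3): dropping pain-rescue days can turn a non-response into a response if those days score higher, and the output-table notes appear to state a different rule

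*SAP*

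**What the plan says.** SAP 6.1.2.3 repeats the primary responder analysis to assess the impact of rescue medication for pain. The subject's "diary will be considered non-evaluable on the days that they received rescue medications". The same approach is used for the 40% and 50% thresholds in FAS-D.

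SAP 4.3.1.1 defines what an evaluable week is. The weekly average divides by the number of days with a pain entry, and "Weekly average will be set missing if there are more than 2 missed diary days over the past 7 days". A week with a missing average is a non-response. Overall response needs "success on 6 or more weeks during the past 12 weeks" and a second condition: "Must have had ≥ 60 diary days over the past 12 weeks". SAP 4.2.3 adds that nothing is imputed for missing diary data when responders are derived.

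SAP 11.1.1 carries a programming note on tables 14.2.1.3.2, 14.2.1.5 and 14.2.1.7: "The subject is considered a non-responder for the days receiving pain medication". The titles of these tables are not visible. All three use FAS-D and each follows the 30%, 40% or 50% analysis.

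Protocol 6.5.3 limits when rescue is allowed: "Rescue medications should only be used starting at Day 1 (Visit 3) or after".

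**The concern.** The purpose of this analysis is to show how far pain rescue affects the responder results. In the visible text it is the only analysis that does so; SAP 5.5.1 summarises rescue use but does not relate it to response.

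SAP 6.1.2.3 does not spell out the recalculation. On the natural reading, a non-evaluable day is handled like a missed day, so one or two rescue days cost the subject nothing. If rescue was taken on her worse days, removing them lowers her weekly average and credits rescue use as improvement. A check on rescue should not be able to do that.

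The table notes point the other way, towards non-response, but the visible text does not say how a day-level non-response enters a weekly average. Two programmers could produce different tables from the same SAP.

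**Working it through.** **Plan figures for context.** The documents give no rescue frequency, no rescue-day scores and no expected size for this analysis. The stated power of about 60% is reproduced and not disputed. For 51% v 31%, 45 per arm, two-sided alpha 0.10, the null standard error is sqrt(2 × 0.41 × 0.59/45) = 0.1037 and the alternative standard error is sqrt(0.51 × 0.49/45 + 0.31 × 0.69/45) = 0.1015. Power is Φ((0.20 − 1.645 × 0.1037)/0.1015) = 61.4%. The 90% confidence interval half-width is 1.645 × 0.1015 = 16.7 points.

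**How many rescue days are free of penalty.** Evaluable days = 7 − missed − rescue, and at least 5 are needed. That allows 2 rescue days with a complete diary, 1 with one missed entry and 0 with two.

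**Worked weeks (assumed scores, baseline 6.0).** Response needs a weekly mean of at most 4.2 (30%), 3.6 (40%) or 3.0 (50%).

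| Threshold | Other days | Rescue days | As recorded | Rescue days dropped |
|---|---|---|---|---|
| 30% | six at 4 | one at 6 | 30/7 = 4.286, 28.6%, no | 24/6 = 4.0, 33.3%, yes |
| 30% | five at 4 | two at 5 | 30/7 = 4.286, 28.6%, no | 20/5 = 4.0, 33.3%, yes |
| 40% | three at 3, three at 4 | one at 5 | 26/7 = 3.714, 38.1%, no | 21/6 = 3.5, 41.7%, yes |
| 50% | six at 3 | one at 4 | 22/7 = 3.143, 47.6%, no | 18/6 = 3.0, 50.0%, yes |
| 30% | 5, 5, 4, 4, 4 | two at 2 | 26/7 = 3.714, 38.1%, yes | 22/5 = 4.4, 26.7%, no |
| 30% | four at 4 | three at 7 | 37/7 = 5.286, 11.9%, no | 4 days left, missing, no |

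The last two rows show the limits: the effect reverses if rescue days score lower, and three rescue days make the week a non-response.

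**Twelve weeks.** Take five weeks at 4 (33.3%), one week from the first row, and six weeks at 5 (16.7%). As recorded, 5 of 12 weeks respond and she is a non-responder. Dropping the single rescue day gives 6 of 12 and she is a responder. She has 84 diary days, or 83 if the dropped day is not counted, so the 60-day condition holds either way.

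**Illustrative size (all inputs assumed).** 30,000 simulated women per arm; baseline mean 6 (between-woman SD 1), daily SD 1.8, week SD 0.5, SD of individual reduction 0.28; arms calibrated to 31% and 51% with 5% missed entries and 10% dropout. Pain-related rescue, with the same rule in both arms, falls on 30, 50 or 80% of scored days with pain ≥ 6 or ≥ 7 and on 3% of other days. Missed entries/dropout are 0/0, 5/10 or 10/10%. That makes 3 × 2 × 3 = 18 scenarios. Changes are in points against the analysis as recorded:

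| Quantity | Dropped days count towards 60 | They do not |
|---|---|---|
| Arm rate, rescue related to pain | −0.2 to +5.9 | −6.7 to +5.2 |
| Arm difference, rescue related to pain | −0.3 to +0.1 | −1.1 to +0.1 |
| Arm rate, rescue unrelated to pain (10 or 20% of days) | −11.5 to −0.2 | −24.3 to −0.2 |

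New responders are 1.6–6.6% of an arm when rescue follows pain and 0.2–1.2% when it does not. A separate simulation with other assumed inputs agrees on direction: 33.9% rises to 36.5–38.8% with pain-driven rescue on 9–17% of days, and stays at 34.0% with unrelated rescue.

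**The case against.** **The direction is assumed.** This stands. The documents hold no rescue-day scores, and the results above run from +5.9 to −24.3 points. A reader might infer that dropping rescue days always inflates response; it does not. The defect is that the rule permits a rescue flag to create a response.

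**The treatment comparison barely moves.** This also stands. SAP 6.1.2.3 is about the comparison between arms, and in the pain-related scenarios the difference shifts by at most 1.1 points against a half-width of 16.7. A reader might infer a bias towards vibegron, but nothing in the documents shows that. Different rescue behaviour by arm at the same pain level was not examined.

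**The conflict with the table notes is inferred.** Partly right. The titles are not visible, a cumulative daily responder is listed in SAP 11.1.3 (listing 16.2.2.12), and its definition may sit in blacked-out text. So one cannot say that the notes are unworkable. But 6.1.2.3 concerns the weekly responder, and position, analysis set and the pain-medication wording all match it.

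**How to score rescue days is a choice of estimand.** True. Dropping them is a legitimate second analysis if labelled as such; it is a poor sole check on rescue.

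**Side points.** The diary prompt covers use "asking if any rescue medication was taken for abdominal pain or stool or pain/stool symptoms", and a combined pain/stool day naturally includes pain. Flagged run-in days would depart from Protocol 6.5.3. Neither is pressed here.

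**Conclusion.** The point holds in a limited form. On the natural reading of SAP 6.1.2.3 with 4.3.1.1, a pain-rescue flag can create a weekly response at all three thresholds and, through the 6-of-12 rule, an overall responder. That is exact arithmetic, conditional on rescue days scoring higher. How often it happens rests on assumed inputs. The mismatch with the table notes is likely but inferred.

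It would go too far to conclude that the primary result, the power or the treatment difference is compromised. The primary analysis does not use this rule, and SAP 4.1.2 treats all efficacy analyses as descriptive. Priority is low to moderate.

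**What to change.** Before unblinding, reconcile SAP 6.1.2.3 and the three table notes to one week-level rule under which a pain-rescue flag cannot turn a non-response into a response, in line with the notes' non-responder intent. State whether rescue days count towards the 5-of-7 and 60-day minimums.

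One option, for this sensitivity analysis only:

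- Score a post-baseline pain-rescue day as the larger of its recorded score and the baseline weekly average. This never lowers a score, so if the day counts are left as recorded it cannot create a response.
- Keep as non-responses the weeks with fewer than 5 rescue-free diary days. Without this, the option is more lenient than the current rule: at baseline 6.0, four days at 1 and three rescue days scored 6 give 22/7 = 3.14, a 47.6% fall and a response, where the current rule gives a non-response.

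With both parts, no week responds that would fail under deletion: if the mean including days at or above baseline meets the threshold, so does the mean without them. Whether the same holds for overall response depends on the 60-day count. Deletion may be kept as a second, labelled analysis.

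The cost is a few lines of SAP text and minor programming. Some weekly responses are lost: seven days at 4 (33.3%) with one flag become (6 × 4 + 6)/7 = 4.286, or 28.6%. Without the 5-day condition, the option lowers arm rates by about 1.3–3.2 points against the analysis as recorded in the pain-related scenarios, and by 4.3–11.7 points if 10–20% of days carry unrelated rescue. Against the current deletion rule the rate may move either way: down by at least 5.9 points where deletion adds 5.9, or up by at least 24.3 − 11.7 = 12.6 where rescue is unrelated to pain and dropped days do not count. The version with the 5-day condition was not simulated; its rates can only be equal or lower. This is an analysis rule and changes no rescue treatment.
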